19.1.2 Analyses

Population: FAS and PP

Stratification: Table: Add the strata as needed in case subjects with dose modification exceeding 20% based on enrolled population as per section 7.3:

- a. Subjects on 1.5 mg only
- b. Subjects on 0.75 mg only
- c. Subjects with any dose modification*

* Subjects who have received at least one dose of 1.5 mg and at least one dose of 0.75 mg

Statistics: The mean change in HbA1c level from baseline to Weeks 12 and 24 for all available data including post-rescue medication values will be analysed using descriptive statistics (mean, median, SD, SE, minimum, maximum, and number with missing values). In addition, for the actual value and change from baseline, a descriptive analysis using LOCF will be performed, using the baseline or 12-week value, if the 24-week value is missing or occurred after use of rescue medication.

For subjects requiring rescue medication, HbA1c values recorded after the first administration of rescue medication will not be

considered for analysis, and these values will be considered as missing.

Note: Rescue medications will be identified by the medical team.

The MMRM will be used for analysis of the change in HbA1c level from baseline to Weeks 12 and 24. An unstructured covariance structure will be used to model the within-patient variability and implicitly adjust for missing data. If this analysis fails to converge, the following covariance structures will be tested in order.

1. Toeplitz with heterogeneity
2. Autoregressive with heterogeneity, by visit
3. Compound symmetry with heterogeneous variances, by visit
4. Toeplitz
5. Autoregressive
6. Compound symmetry without heterogeneous variances, by visit

From the above covariance structures, the first covariance structure that converges will be used. The Kenward-Roger approximation will be used to estimate denominator degrees of freedom. Significance tests will be based on least-squares mean using Type III sum of squares.

The MMRM for each of the endpoints will include the respective baseline score and any covariates. Baseline insulin level, insulin regimen and insulin use(yes/no) will be included as covariates in the model if convergence is met. If convergence is not met with baseline insulin level and insulin regimen as covariates, then only insulin use(yes/no) will be used.

If convergence is not met in the MMRM, the change in HbA1c level from baseline to Week 24 will be analysed using the general linear model. The general linear model will evaluate the change from baseline in HbA1c level as the dependent variable and the

baseline value of HbA1c as covariate. The LOCF method of missing value imputation will be used.

Additionally, all the analysis will be repeated for the below mentioned subgroups:

- age (<65 year and \geq 65 year)
- HbA1c (<8.5 and \geq 8.5)
- Sex (Female and male)
- BMI category (<27 kg/m²) and \geq 27 kg/m²)

Forest plot of Mean change from baseline of HbA1c for overall and subgroup will be presented. Line plot will be plotted to show the trend of HbA1c lowering. Mean change values will be used by timepoint for plotting.

20. Exploratory endpoint**20.1 Mean change in body weight from baseline to Week 24****20.1.1 Variables and derivations**

Variables:

- Weight (in Kgs)

Derivations:

- Weight (in Kgs) results between visit baseline visit 2 (week 0) and visit 8 (week 24) will be used.

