5.1. Inclusion Criteria

Participants are eligible to be included in the study only if all the following criteria apply:

Age

1. Participants are 18 years of age or older, at the time of signing the informed consent.

Type of Participant and Disease Characteristics

2. Participants have a diagnosis of T2DM for at least 1 year, currently treated with stable doses of oral antihyperglycemic medications with or without stable doses of basal or premix insulin for the last 3 months prior to screening. Premix insulin is allowed up to twice daily in the screening period to be taken up further. Doses of other OHAs will be optimized as per investigator's discretion. Patients on thrice-daily premix insulin or full basal bolus insulin (insulin regimen, 3 to 4 times daily) therapy are excluded from the study.
3. Participants have HbA1c $\geq 7.5\%$ and $\leq 11.5\%$, both inclusive, at screening.

Weight/BMI

4. Participants have BMI $\geq 23 \text{ kg/m}^2$.

Sex and Contraceptive/Barrier Requirements

Contraceptive use by participants should be consistent with local regulations regarding the methods of contraception for those participating in clinical studies.

5. Male study participants: No male contraception is required except in compliance with specific local government study requirements. Female study participants: For the contraception requirements of this protocol, see Section 10.4.

Informed Consent

6. Participants are capable of giving signed informed consent as described in Appendix 1, which includes compliance with the requirements and restrictions listed in the ICF and in this protocol.

Other Inclusions

7. Residents of India

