The analysis for other continuous exploratory efficacy and safety measurements and continuous laboratory measures at 24 weeks will use the MMRM. It will be used to model change from baseline in FBG and any other safety or efficacy endpoints. Missing data will be assumed missing at random and will be accommodated by the MMRM.

The MMRM using restricted maximum likelihood will be done for analyses of change in FBG from baseline (note: statistical comparison will not be conducted) during the entire study period.

The MMRM could be repeated for other safety and efficacy endpoints.

For FBG, summary statistics will be provided for the observed value and change from baseline value based on the MMRM.

An unstructured covariance structure will be used to model the within-patient variability and implicitly adjust for missing data. If this analysis fails to converge, the following covariance structures will be tested in order.

1. Toeplitz with heterogeneity
2. Autoregressive with heterogeneity, by visit
3. Compound symmetry with heterogeneous variances, by visit
4. Toeplitz

5. Autoregressive
6. Compound symmetry without heterogeneous variances, by visit

The first covariance structure that converges will be used. The Kenward-Roger approximation will be used to estimate denominator degrees of freedom. Significance tests will be based on least-squares mean using Type III sum of squares.

If none of the models converge then an analysis of covariance using LOCF imputation with similar terms as in the MMRM (except no terms that include visit) will be used in its place.

The MMRM for each of the endpoints will include the respective baseline score and any covariate.

Baseline insulin use will be included as covariate in the model if convergence is met. Dose will be included as a covariate in the models, if appropriate. Details will be included in the SAP. Handling of missing, unused, and spurious data are addressed prospectively in the overall statistical methods described in the protocol and in the SAP, where appropriate. Adjustments to the planned analyses are described in the final CSR.

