18.1.2 Analyses

Population: FAS and PP

Stratification: Table: Add the strata as needed in case subjects with dose modification exceeding 20% based on enrolled population as per section 7.3:

- a. Subjects on 1.5 mg only
- b. Subjects on 0.75 mg only
- c. Subjects with any dose modification*

* Subjects who have received at least one dose of 1.5 mg and at least one dose of 0.75 mg

Listing: by subject and events

Statistics: The incidence of AEs (including deaths, SAEs, TEAEs, hypoglycemia, including severe hypoglycemia and GI disorders) will be summarised as frequency and percentages.

The listings will be presented for the hypoglycaemia events.

The incidence of AE (death, SAE, and TEAE) will be summarized. The rate per year (i.e., number of deaths, SAE, and TEAEs per subject per year over the study period) will be assessed using a negative binomial model with the log of the study treatment exposure time as an offset variable and the model will be performed as per details mentioned below.

The incidence of hypoglycemic AEs will be summarized. The number of hypoglycemic events per subject over the study period will be analysed as continuous variables and will be summarized as (n, mean, standard deviation, standard error, median, minimum, maximum).

The rate per year of hypoglycemic events, that is, the number of hypoglycemic events per patient-year (365.25 days) will be assessed using a negative binomial model, with baseline HbA1c and baseline insulin usage as covariates and the log of the study treatment exposure time as an offset variable.

The Negative Binomial Model i.e., the generalized linear model will be used with baseline HbA1c and baseline insulin usage and the log of the study treatment exposure time as offset variable.

The incidence rate, least square mean and corresponding 95% confidence interval will be provided for table.

Also, in case we have more than 20% data missing in any of the covariate, we will repeat the analysis after omitting the impacted covariate.

In case of multiple doses of insulin uptake per day, a sum of insulin per day will be used as the baseline insulin covariate. Regimen for subjects with more than 1 regimen type per day will be reviewed by

medical team. Insulin Dose level for subjects not on insulin will be considered as 0 and the corresponding regimen as 'Non'.

In case convergence is not met with the above variables, only baseline HbA1c and baseline insulin usage(Yes/No) will be considered.

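### The HbA1c MMRM in SAP 19.1.2 carries both insulin use (yes/no) and insulin regimen, which are redundant; with default weights the LS mean change is then non-estimable, and the convergence-only fallback does not catch this

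*SAP*

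**What the plan says.** SAP 19.1.2 gives the covariates for the HbA1c MMRM: "Baseline insulin level, insulin regimen and insulin use(yes/no) will be included as covariates in the model if convergence is met". The next sentence gives the only route to a smaller set: "If convergence is not met with baseline insulin level and insulin regimen as covariates, then only insulin use(yes/no) will be used". On inference it says: "Significance tests will be based on least-squares mean using Type III sum of squares".

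Section 19.1.2 has no coding rule for patients not on insulin. The only one in the SAP is in 18.1.2, written for the negative binomial model: "Insulin Dose level for subjects not on insulin will be considered as 0 and the corresponding regimen as" 'Non'. The same section defines the dose covariate: "a sum of insulin per day will be used as the baseline insulin covariate".

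Protocol 9.4.1 names a single insulin term for the MMRM: "Baseline insulin use will be included as covariate in the model if convergence is met". It leaves further details to the SAP. SAP section 5 reports no changes to the planned analyses.

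The SAP names SAS 9.4 or later (7.6). It does not say which insulin terms are classification variables, how LS means are weighted, or what happens if the model is rank-deficient.

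**The concern.** Under the 18.1.2 coding, the indicator for use = No and the indicator for regimen = 'Non' are the same column. A model holding both is over-parameterised. Mixed-model software usually copes by means of a generalized inverse, so the fit completes, but some linear combinations of the parameters are no longer uniquely defined.

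In a two-arm trial a treatment difference would survive such an alias between covariates. This trial has one arm, so the model's result is the LS mean change itself, and that is the quantity at risk. The plan's safeguard looks for non-convergence, which is a different failure.

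**Working it through.** **Inputs from the documents**

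- Regimen levels: Protocol 5.1 admits patients "with or without stable doses of basal or premix insulin for the last 3 months prior to screening". That gives none, basal and premix, so k = 3. A note to Protocol Figure 6.1 also mentions basal plus, which would make k = 4.
- Post-baseline HbA1c visits in the model: Weeks 12 and 24 (SAP 19.1.2).
- Sample size (Protocol 9.6): 250 × (1 − 0.20) = 200 treated and 200 × (1 − 0.20) = 160 completers. Both stated figures reproduce. The check uses n = 160. The plan gives no figure for the HbA1c model itself.

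**Assumptions not in the documents**

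40% insulin users, regimens split evenly, gamma-distributed doses, 20% of Week 24 values missing in the convergence check, and assumed HbA1c responses.

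**Step 1: rank.** Fixed effects are intercept, visit, baseline HbA1c, use, regimen (k = 3 with 'Non') and dose.

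| Insulin terms in the model | Rank |
|---|---|
| use + regimen + dose | 6 |
| regimen + dose | 6 |
| use + regimen | 5 |
| use + dose | 5 |

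Use adds 6 − 6 = 0 degrees of freedom, so it has no Type III test. Dose adds 6 − 5 = 1, so it is not aliased.

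**Step 2: estimability.** With use and regimen both as classification terms, putting +1 on use = No and −1 on regimen = 'Non' gives zero for every patient. An estimable LS mean must therefore give those two cells equal weight.

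- Equal weights, k = 3: 1/2 − 1/3 = 1/6, so not estimable.
- Equal weights, k = 4: 1/2 − 1/4 = 1/4. With k = 5: 1/2 − 1/5 = 3/10. Neither is estimable.
- Equal weights, k = 2: 1/2 − 1/2 = 0, so estimable.
- Observed margins, with p₀ the share not on insulin: p₀ − p₀ = 0, so estimable for any k.

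If use enters as a numeric 0/1 term with mean p, the condition becomes p + 1/k − 1 = 0. For k = 3 this needs p = 2/3 exactly. At about 40% users it gives 0.40 + 0.33 − 1 = −0.27, so not estimable.

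**Step 3: what non-estimable means.** In one simulated dataset, three least-squares solutions with the same fit (residual sum of squares 297.67) gave equal-weight Week 24 LS means of −1.289, −1.254 and −1.280. The spread is 1.289 − 1.254 = 0.035. The observed-margin LS mean was −1.302 in all three.

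**Step 4: does the fallback fire?** A REML fit with an unstructured 2 × 2 covariance and a generalized inverse converged in 60 of 60 simulated datasets. The aliasing did not trip the convergence rule.

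**Step 5: after the fix (k = 3).** The default LS mean is estimable with use alone, regimen alone, use + dose, or regimen + dose. The last has the same rank as the three-term model, so nothing is lost.

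**The case against.** The strongest reply is that level and regimen are the full set and use (yes/no) is only the fallback. The sentence after the covariate list in SAP 19.1.2 reads that way. SAP 18.1.2 falls back to usage yes/no, and 20.1.2, 20.2.2 and 20.3.2 follow the same pattern. On that reading there is no alias. It may well be what was intended, but the covariate sentence lists all three terms, so it needs correcting either way.

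A second reply is that the failing configuration is not fully written down. This stands in part. Non-estimability needs the 'Non' coding carried over from 18.1.2, at least three regimen levels and default weights, and 19.1.2 fixes none of these. Leaving regimen uncoded for non-users would not help, however: they would normally be dropped as missing, leaving use constant.

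A third reply is that Protocol 9.4.1 delegates detail to the SAP, so expanding insulin use into dose and regimen need not be a departure. That is fair. The protocol's single term is cited here as one available remedy.

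A reader might also go further than the documents allow:

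- **All three insulin terms are aliased.** Dose is not; removing it lowers the rank from 6 to 5.
- **The fallback can never operate.** Another cause of non-convergence, for instance in a small subgroup, could still trigger it.
- **The secondary endpoint would have no result.** SAP 19.1.2 also provides descriptive mean changes at Weeks 12 and 24 and an LOCF summary, and neither needs the model.
- **The remedy would be picked after seeing results.** Nothing in the documents shows this; a rank problem is visible on test data before database lock.

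**Conclusion.** The point holds in limited form. As worded, the HbA1c model contains one redundant term, and the convergence rule does not detect the redundancy. Under the 18.1.2 coding, with at least three regimen levels and equal-weight LS means, the Week 24 LS mean change is not uniquely defined. The mismatch in weights is 1/6 at three levels. The 0.035 spread in Step 3 only illustrates this on assumed data and is not a forecast of bias; in practice software would be expected to flag the estimate as non-estimable.

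The consequence is moderate. The endpoint is secondary, the study has one arm and no formal hypotheses (Protocol 9.1), and the descriptive results stand. The redundancy of use and regimen rests only on the coding. Non-estimability also depends on the number of levels and the weights. The point is still worth correcting, because a stated rule misfires and removing the redundant term loses no information.

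**What to change.** In SAP 19.1.2:

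1. Delete the redundant term. Use either insulin use (yes/no) alone, as Protocol 9.4.1 names, or regimen plus total daily dose with use (yes/no) only as the fallback.
2. State that the 'Non' and zero-dose coding in 18.1.2 also applies to the MMRM.
3. Extend the fallback trigger to a non-estimable LS mean as well as non-convergence.

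Observed-margin LS means are optional. They would make the estimate describe the trial population, and they are estimable even with all three terms, but that is a choice of target rather than a required correction. Whichever weights are used should be stated.

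The cost is a few sentences in the SAP and the matching model statement. No new data are needed.

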20.1.2 Analyses

Population: FAS and PP

Stratification: Table: Add the strata as needed in case subjects with dose modification exceeding 20% based on enrolled population:

- Subjects on 1.5 mg only
- Subjects on 0.75 mg only
- Subjects with any dose modification*

* Subjects who have received at least one dose of 1.5 mg and at least one dose of 0.75 mg

Statistics: The actual values and change from baseline will be summarized by descriptive statistics (n, missing values, mean, median, SD, SE, minimum, and maximum) by visit. No multiplicity adjustment will be done.

The analysis of Mean change in weight at 24 weeks will use the MMRM. Missing data will be assumed missing at random and will be accommodated by the MMRM. The MMRM using restricted maximum likelihood will be done for analyses (note: statistical comparison will not be conducted) during the entire study period. An unstructured covariance structure will be used to model the within-patient variability and implicitly adjust for missing data. If

this analysis fails to converge, the following covariance structures will be tested in order.

1. Toeplitz with heterogeneity
2. Autoregressive with heterogeneity, by visit
3. Compound symmetry with heterogeneous variances, by visit
4. Toeplitz
5. Autoregressive
6. Compound symmetry without heterogeneous variances, by visit

The first covariance structure that converges will be used. The Kenward-Roger approximation will be used to estimate denominator degrees of freedom. Significance tests will be based on least-squares mean using Type III sum of squares.

If none of the models converge then an analysis of covariance using LOCF imputation with similar terms as in the MMRM (except no terms that include visit) will be used in its place. The model will evaluate the change from baseline in weight as the dependent variable and the baseline value of weight as covariate.

The MMRM for each of the endpoints will include the respective baseline score and any covariate. Baseline HbA1c and baseline insulin use will be included as covariate in the model if convergence is met. If convergence is not met with baseline insulin level and insulin regimen as covariates, then only insulin use(yes/no) will be used for insulin usage.

Additionally, all the analysis will be repeated for the below mentioned subgroups:

- age (<65 year and \geq 65 year)
- HbA1c (<8.5 and \geq 8.5)
- Sex (Female and male)
- BMI category (<27 kg/m²) and \geq 27 kg/m²)

Line plot will be plotted to show the trend of body weight lowering.
Mean change values will be used by timepoint for plotting.

20.2 Mean change in FBG from baseline to Week 24

20.2.1 Variables and derivations

Variables:

- FBG results

Derivations:

- FBG results between visit baseline visit 2 (week 0) and visit 8 (week 24) will be used.

20.2.2 Analyses

Population: FAS and PP

Stratification: Table: Add the strata as needed in case subjects with dose modification exceeding 20% based on enrolled population:

- a. Subjects on 1.5 mg only
- b. Subjects on 0.75 mg only
- c. Subjects with any dose modification*

* Subjects who have received at least one dose of 1.5 mg and at least one dose of 0.75 mg

Statistics: The actual values and change from baseline will be summarized by descriptive statistics (n, missing values, mean, median, SD, SE, minimum, and maximum) by visit. No multiplicity adjustment will be done.

The analysis of Mean change in FBG at 24 weeks will use the MMRM. Missing data will be assumed missing at random and will be accommodated by the MMRM. The MMRM using restricted maximum likelihood will be done for analyses (note: statistical comparison will not be conducted) during the entire study period. An unstructured covariance structure will be used to model the within-patient variability and implicitly adjust for missing data. If this analysis fails to converge, the following covariance structures will be tested in order.

1. Toeplitz with heterogeneity
2. Autoregressive with heterogeneity, by visit
3. Compound symmetry with heterogeneous variances, by visit
4. Toeplitz
5. Autoregressive
6. Compound symmetry without heterogeneous variances, by visit

The first covariance structure that converges will be used. The Kenward-Roger approximation will be used to estimate denominator degrees of freedom. Significance tests will be based on least-squares mean using Type III sum of squares.

If none of the models converge then an analysis of covariance using LOCF imputation with similar terms as in the MMRM (except no terms that include visit) will be used in its place. The model will evaluate the change from baseline in FBG as the dependent variable and the baseline value of FBG as covariate.

The MMRM for each of the endpoints will include the respective baseline score and any covariate. Baseline HbA1c use and baseline insulin use will be included as covariate in the model if convergence is met. If convergence is not met with baseline insulin level and insulin regimen as covariates, then just insulin use(yes/no) will be used for insulin usage.

Additionally, all the analysis will be repeated for the below mentioned subgroups:

- age (<65 year and \geq 65 year)
- HbA1c (<8.5 and \geq 8.5)
- Sex (Female and male)
- BMI category (<27 kg/m²) and \geq 27 kg/m²)

Line plot will be plotted to show the trend of FBG lowering. Mean change values will be used by timepoint for plotting.

20.3 Mean change in systolic blood pressure, diastolic blood pressure, and pulse rate from baseline to Week 24

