7.1. Discontinuation of Study Intervention

When necessary, a participant may be permanently discontinued from study intervention. If so, the participant will remain in the study and follow procedures for remaining study visits, as shown in the SoA.

Participants who stop dulaglutide permanently may receive another glucose-lowering medication at the investigator discretion. The new glucose-lowering medication will be recorded on the appropriate CRF.

A participant should be permanently discontinued from study intervention if the participant

- becomes pregnant during the study
- requests to discontinue dulaglutide
- did not take dulaglutide for more than 4 consecutive weeks or missed more than 4 consecutive doses of dulaglutide at any time during the study
- is inadvertently enrolled (this would be decided in consultation with the Sponsor's medical officer), or
- should permanently discontinue the study intervention for safety reasons, in the opinion of the investigator.

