8.1. Efficacy Assessments

Efficacy will be measured by HbA1c and fasting glucose. See Section 3 for specific efficacy endpoints.

Glucose monitoring

Participants will receive a sponsor-approved glucometer and related testing supplies for use during the study.

Site personnel will train the participant on correct use of the glucometer for self-monitoring BG and reporting of hypoglycemia data in the paper diary.

As directed by the investigator, they may use the glucometer

- whenever hypoglycemia is experienced or suspected
- when there is awareness of increased risk related to changes in dietary intake, physical activity, or inadvertent or atypical insulin dosing
- when patients take concomitant insulin therapy or sulfonylureas.

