9.4.3. Secondary Endpoints Analysis

Change in HbA1c from baseline to 24 weeks of therapy with dulaglutide 1.5 or 0.75 mg

The change in HbA1c level from baseline to Weeks 12 and 24 for all available data including post-rescue medication values will be analyzed using descriptive statistics (mean, median, SD, SE, minimum, maximum, and number with missing values). In addition, for the actual value and change from baseline, a descriptive analysis using LOCF will be performed, using the baseline or 12-week value, if the 24-week value is missing or occurred after use of rescue medication.

For subjects requiring rescue medication (see Section 6.1.1), HbA1c values recorded after the first administration of rescue medication will not be considered for analysis, and these values will be considered as missing. The MMRM, as described in Section 9.4.1 will be used for analysis of the change in HbA1c level from baseline to Weeks 12 and 24.

If convergence is not met in the MMRM, the change in HbA1c level from baseline to Week 24 will be analyzed using the general linear model for the FAS population. The general linear model will evaluate the change from baseline in HbA1c level as the dependent variable and the baseline value of HbA1c as covariate. The LOCF method of missing value imputation will be used.

FAS population will be used for analysis as per planned treatment.

The analyses will be repeated for the per-protocol population.

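### HbA1c recorded after rescue medication is removed from the MMRM, but FBG recorded after rescue is kept and read as change on dulaglutide

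*SAP*

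**What the plan says.** Protocol 8.1 names two efficacy measures together: "Efficacy will be measured by HbA1c and fasting glucose".

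**HbA1c (secondary).** Protocol 9.4.3 states that "HbA1c values recorded after the first administration of rescue medication will not be considered for analysis, and these values will be considered as missing", and then specifies the MMRM. SAP 19.1.2 repeats the rule. Both also plan a descriptive summary that keeps everything; in the SAP's words, change "for all available data including post-rescue medication values will be analysed using descriptive statistics".

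**FBG (exploratory).** SAP 20.2.1 takes the FBG results from Visit 2 to Visit 8 without exception. SAP 20.2.2 then states: "The analysis of Mean change in FBG at 24 weeks will use the MMRM". Neither the MMRM, its ANCOVA/LOCF fallback nor the by-visit descriptive summary mentions rescue. Protocol 9.4.1 and 9.4.4 add no rule.

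**What may be taken during the trial.** Protocol 6.1.1 permits rescue at any time, with a request to delay it for the first 4 weeks if possible. Protocol 6.8 lets the investigator treat hyperglycemia with insulin or oral drugs. Under protocol 7.1, patients who permanently stop dulaglutide remain in the study for their visits, and "Participants who stop dulaglutide permanently may receive another glucose-lowering medication at the investigator discretion".

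**What rescue means for analysis.** SAP 19.1.2 leaves this to the medical team. SAP 14.1 tabulates rescue therapy separately from drugs used in diabetes.

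**The concern.** In a single-arm trial the mean change from baseline is the whole efficacy result, and no comparator absorbs the effect of added treatment. A drug added on top of dulaglutide because glucose is high lowers the next FBG, and the model credits that fall to dulaglutide. The plan guards against this for HbA1c and not for FBG, so the two glycaemic results in one report would answer different questions without saying so.

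A second gap touches both measures. A patient who has stopped dulaglutide can still supply Week 12 or Week 24 values, with or without a replacement drug, and the full analysis set has no on-treatment condition. The plan does not say whether those values belong in the models. If they are kept without comment, they are attributed to a drug that the patient no longer takes.

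**Working it through.** **1. The plan's own figures.** Protocol 9.6: 250 × (1 − 0.20) = 200 treated; 200 × (1 − 0.20) = 160 at the end of the study. Both reproduce. Neither document gives a rescue rate or an effect size for rescue drugs, so the size below rests on assumptions.

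**2. The passages side by side.**

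| | HbA1c | FBG |
|---|---|---|
| All-data descriptive summary | Yes, post-rescue values expressly included | Yes, no exclusion stated |
| MMRM after first rescue | Set to missing | Kept (no rule) |
| Fallback if the MMRM fails | Covered by the set-to-missing rule | No rule |
| Values after stopping dulaglutide | Not addressed | Not addressed |

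SAP 8.2 has one general sentence replacing a Week 24 value that follows rescue. It governs a descriptive LOCF analysis only. Its MMRM sentence has no rescue clause, and SAP 20.2.2 plans no descriptive LOCF analysis of FBG.

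**3. Size of the FBG shift.** Let f be the share of patients whose Week 24 FBG is on rescue, and d the extra fall that the added drug produces. Each such value is lower by d, so

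overstatement of the mean fall = f × d.

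- Low end: 0.05 × 30 = 1.5 mg/dL
- High end: 0.15 × 60 = 9 mg/dL

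With 160 patients, these shares are 160 × 0.05 = 8 and 160 × 0.15 = 24 patients.

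**4. Does the HbA1c rule remove the shift?** A simulation used 160 patients, visits at Weeks 12 and 24, a true mean change of about −30 mg/dL, and rescue given to those with the highest Week 12 FBG. It compared keeping all Week 24 values with treating post-rescue values as missing at random.

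| f | d (mg/dL) | All values kept | Post-rescue set to missing | True mean |
|---|---|---|---|---|
| 5% | 20 | −31.03 | −30.05 | −30.03 |
| 10% | 40 | −33.90 | −29.97 | −29.90 |
| 20% | 40 | −37.91 | −29.96 | −29.91 |

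The gap between the all-values result and the true mean is f × d in each row (1, 4 and 8 mg/dL). Setting post-rescue values to missing removes it. In this simulation missing at random held by construction, because rescue depended on an observed Week 12 value.

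**5. Values after stopping dulaglutide.** A replacement drug starts once dulaglutide has been stopped. If D is the dulaglutide effect that is lost and d the effect of the replacement, the shift relative to staying on dulaglutide is f × (d − D). It overstates the fall if d > D and understates it if d < D. With no replacement drug, d = 0 and the fall is understated. The documents fix neither d nor D, so no size can be given.

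**The case against.** The strongest reply is that keeping every value is a legitimate treatment-policy choice, especially for an exploratory endpoint in a safety study with no hypothesis. Protocol 9.4.1 and SAP 20.2.2 also note that no statistical comparison will be made for FBG. This stands as to importance. It does not settle the point: the plan states no such choice, makes the opposite one for HbA1c, and in SAP 20.2.2 also specifies significance tests on least-squares means.

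The per-protocol repeat helps in part. It requires 24 weeks of treatment, 80% compliance and no gap over 15 days, so it removes most early stoppers. No criterion names rescue, so a rescued patient who stays on dulaglutide remains in it.

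Several stronger readings are tempting, and the documents do not support them:

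- A reader might infer that replacement drugs always flatter dulaglutide. Step 5 shows that the sign is unknown.
- A reader might infer that HbA1c on added or replacement drugs certainly stays in the MMRM. The medical team could class those drugs as rescue; the matter is undecided. Protocol 7.2 does not decide it either: it withdraws patients who need a prohibited agent, but the protocol lists no such agents.
- A reader might take the sentence in inclusion criterion 2 that begins "Doses of other OHAs will be optimized as per" as evidence of dose increases during treatment. It is an eligibility statement that follows one about the screening period, and does not clearly describe on-treatment changes.
- A reader might say that the HbA1c rule exists because the aim is the change while on dulaglutide. Neither document gives a reason for the rule.

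It is also fair to say that missing at random may fail. FBG after baseline is taken only at Weeks 12 and 24. A patient rescued before Week 12 would have no usable later value and would be represented by the others, which could enlarge the estimated fall.

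**Conclusion.** The FBG gap is real. The FBG MMRM and its fallback keep values measured on rescue drugs, while the HbA1c MMRM discards them, and nothing elsewhere in the plan closes the difference. For drugs added to continuing dulaglutide the bias runs one way: the mean FBG fall is overstated by f × d. That is about 1.5 to 9 mg/dL if 5 to 15% of patients are affected and the added drug lowers FBG by 30 to 60 mg/dL. Both ranges are assumptions.

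The handling of HbA1c and FBG after permanent discontinuation is unspecified. That is a misattribution problem of unknown direction, and no figure should be attached to it.

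The consequence is for interpretation of one exploratory and one secondary endpoint. The primary safety endpoints and the sample size are not affected. This is a cheap improvement, not a flaw in the trial's main purpose.

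**What to change.** 1. In SAP 20.2.2, set FBG recorded after the first rescue medication to missing in the MMRM and in the ANCOVA/LOCF fallback, as SAP 19.1.2 does for HbA1c.
2. Keep the descriptive FBG summary on all data, label it as including post-rescue values, and present it as the sensitivity result.
3. In SAP 19.1.2 and 20.2.2, state before database lock that glucose-lowering drugs added for hyperglycemia count as rescue for analysis. This is a data classification only and changes nothing in patient care.
4. In the same two sections, state one rule for HbA1c and FBG values taken after permanent discontinuation of dulaglutide. Apply it alike to both measures, whether or not a replacement drug is started.

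**Cost.** SAP wording and derived dates for first rescue and for permanent discontinuation. The protocol already requires rescue use, concomitant medication dates and replacement drugs to be recorded, and the HbA1c rule already needs the rescue date. Protocol 9.4.4 leaves the detail of exploratory analyses to the SAP.

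**Downside.** Fewer Week 24 values enter the models, and the result leans on missing at random, most heavily for patients rescued before Week 12. That is why the all-data result should stay beside it.
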